Non-Interventional Study Protocol

Doc. No.: UXX-XXXX

BI Study No.:	1218.104
BI Investigational Product(s):	Linagliptin
Title:	A regulatory requirement non interventional study to monitor the safety and effectiveness of Trajenta (Linagliptin , 5 mg, q.d) in Korean patients with type 2 diabetes mellitus (SELINA study)
Clinical Phase:	IV
Trial Clinical Monitor:	 Phone:  Fax: 
Principal Investigator:	Not Applicable
Status:	Final protocol (Revised protocol)
Version and Date:	Version: 2.1 Date: 22 Feb 2017
Page 1 of 29	
Proprietary confidential information. © 2017 Boehringer Ingelheim International GmbH or one or more of its affiliated companies. All rights reserved. This document may not - in full or in part - be passed on, reproduced, published or otherwise used without prior written permission.	

Proprietary confidential information. © 2017 Boehringer Ingelheim International GmbH or one or more of its affiliated companies.

NON-INTERVENTIONAL STUDY PROTOCOL SYNOPSIS

Name of company/Marketing Authorisation Holder: Boehringer Ingelheim Korea		Tabulated Study Protocol	
Name of finished product: Trajenta			
Name of active ingredient: Linagliptin			
Protocol date: 1 December 2011	Trial number: 1218.104/UXX-XXXX		Revision date: 22 Feb 2017
Title of study:		A regulatory requirement non interventional study to monitor the safety and effectiveness of Trajenta (Linagliptin , 5 mg, q.d) in Korean patients with type 2 diabetes mellitus (SELINA study)	
Principal Investigator:		To be decided	
Study site(s) :		Multi-centre study	
Clinical phase:		IV	
Objectives:		To monitor the safety profile and effectiveness of linagliptin in Korean patients with type 2 diabetes mellitus in a routine clinical practice setting	
Methodology:		Prospective, non-interventional, open-label, multi-centre national study	
No. of patients:			
Total entered:		3,000 approximately	
each treatment:		Single arm (N=3,000 approximately)	
Diagnosis:		Patients diagnosed with type 2 diabetes mellitus	
Main criteria for inclusion:		
 1) No previous exposure to Trajenta 2) Patients who have been started on Trajenta in accordance with the approved label in Korea 3) No current participation in clinical trials 4) Patients who have signed on the data release consent form 	
Test product(s) :		Linagliptin	
dose:		5 mg q.d	
mode of admin. :		Oral administration	
Comparator product(s): Not applicable			
dose:			
mode of admin. :			

Proprietary confidential information. © 2017 Boehringer Ingelheim International GmbH or one or more of its affiliated companies.

Name of company/Marketing Authorisation Holder: Boehringer Ingelheim Korea		Tabulated Study Protocol	
Name of finished product: Trajenta			
Name of active ingredient: Linagliptin			
Protocol date: 1 December 2011	Trial number: 1218.104/UXX-XXXX		Revision date: 22 Feb 2017
Duration of treatment:	1) Treatment duration for short-term surveillance: 12±2 weeks, long-term surveillance: 24±2 weeks. 2) Study duration: 6 years. (KFDA set Trajenta re-examination period from 14 Sep 2011 to 13 Sep 2017. Interim report planned biannually for the initial two years and annually thereafter by Dec 2017.)		
Criteria for effectiveness:	1. Main endpoint 1) Change from baseline in HbA1c after 24 weeks of treatment. 2. Other endpoint 1) Occurrence of treat to target effectiveness response, that is an HbA1c under treatment of < 6.5% after 24 weeks of treatment. 2) Occurrence of relative effectiveness response (HbA _{1c} lowering by at least 0.5% after 24 weeks) 3) Change from baseline in fasting plasma glucose (FPG) after 24 weeks of treatment		
Criteria for safety:	All reported adverse events including hypoglycemic events in patients who take at least one dose of Trajenta will be noted. Endpoints pertaining to safety will be presented as incidence rates of adverse events		
Statistical methods:	Descriptive statistics		

FLOW CHART

Data points	Baseline	Follow-up 1	Follow-up 2
Visit Number	1	2	3
Week/s	0	12±2	24±2
Diagnosis	X		
Inclusion / exclusion criteria	X		
Demographics	X		
Diabetes mellitus complications	X		
Other medical history	X		
Anti-hyperglycemic agents	X	X	X
Concomitant medications	X	X	X
Trajenta administration status	X	X	X
Renal function	X [^]		
Effectiveness endpoints	X	X	X
Changes in lab tests		X [^]	X [^]
Adverse events		X	X
Study completion		X	X

[^]: If applicable.

TABLE OF CONTENTS

TITLE PAGE	오류! 책갈피가 정의되어 있지 않습니다.
NON-INTERVENTIONAL STUDY PROTOCOL SYNOPSIS	2
FLOW CHART	4
TABLE OF CONTENTS	5
ABBREVIATIONS	8
1. INTRODUCTION	9
1.1 MEDICAL BACKGROUND	9
1.2 DRUG PROFILE	9
2. RATIONALE, OBJECTIVES, AND BENEFIT-RISK ASSESSMENT	10
2.1 RATIONALE FOR PERFORMING THE STUDY	10
2.2 STUDY OBJECTIVES	10
2.2.1 Primary objective	10
2.2.2 Secondary objective	10
2.3 BENEFIT-RISK ASSESSMENT	10
3. DESCRIPTION OF DESIGN AND STUDY POPULATION	11
3.1 OVERALL DESIGN AND PLAN	11
3.1.1 Administrative structure of the study	11

1. INTRODUCTION

1.1 MEDICAL BACKGROUND

Type 2 diabetes mellitus (T2DM) accounts for 90% to 95% of all cases of diabetes and is an increasingly prevalent disease with an estimated 180 million affected people worldwide. Its incidence is expected to double during the next 20 years (R09-4240). In Korea, the prevalence of T2DM patient was 9% in 2010 according to the Diabetes Atlas 4th edition from International Diabetes Foundation.¹ Complications induced by hyperglycaemia are currently the most frequent cause of adult-onset loss of vision, renal failure, and non-traumatic lower extremity amputations in the industrialized world. T2DM is also associated with macrovascular complications with a 2- to 4-fold increase in cardiovascular disease risk. The high frequency of complications leads to a significant reduction of life expectancy (R09-4241).

Although several antidiabetic compounds have been developed to improve glucose control and attenuate the metabolic derangements that accompany uncontrolled T2DM, none of these compounds has been able to maintain long-term glycaemic control.

The improved understanding of the incretin effect has contributed to the development of a new class of antidiabetic agents. The incretin effect results from glucagon like peptide-1 (GLP-1) and glucose dependent insulinotropic peptide (GIP), two intestinal peptides that are released in the presence of glucose or nutrients in the gut. GLP-1 stimulates insulin secretion, thereby augmenting glucose-stimulated insulin release. However, there is little risk of hypoglycaemia due to GLP-1 because GLP-1 activity decreases when glucose concentrations fall below 55 milligrams per deciLiter (mg/dL). Normally, GLP-1 is almost instantaneously inactivated by the enzyme DPP-4 that is widely expressed in many tissues including kidney, liver, intestine, lymphocytes and vascular endothelial cells. Therefore, inhibiting DPP-4 would prolong the activity of GLP-1 for stimulating insulin secretion.

Linagliptin is a potent inhibitor of DPP-4 activity and prolongs the half-life of GLP-1. This has been shown in vitro, in various animal models, and in clinical trials. Linagliptin is an orally available compound with a low risk for hypoglycaemic episodes (U04-1767-09).

1.2 DRUG PROFILE

Linagliptin is an orally administered, highly selective DPP-4 inhibitor which is primarily excreted via bile and gut for the treatment of patients with T2DM²; its pharmacokinetic and pharmacodynamic profile make it suitable for once-daily dosing (P08-06359, P09-09556).

2. RATIONALE, OBJECTIVES, AND BENEFIT-RISK ASSESSMENT

2.1 RATIONALE FOR PERFORMING THE STUDY

According to the local regulations, when a new chemical entity (NCE) is registered, a regulatory non interventional study (rNIS) of an extended period (4 or 6 years) should be conducted. Such rNIS can provide supplementary data to monitor the safety of NCEs in a real-life situation. Data collected in randomised clinical trials with strict inclusion/exclusion criteria and rigorous monitoring schemes have limitations.

This is a prospective, non-interventional, open-label, multi-centre study. It will provide additional safety information of Trajenta in Korean patients with type 2 diabetes mellitus in routine clinical settings.

2.2 STUDY OBJECTIVES

2.2.1 Primary objective

The primary objective of this study is to monitor the safety profile of Trajenta in Korean patients with type 2 diabetes mellitus (T2DM) in a routine clinical setting.

2.2.2 Secondary objective

The secondary objective of the study is to monitor the effectiveness of Trajenta by evaluating the change from baseline to endpoint in the glycosylated hemoglobin (HbA_{1c}), fasting plasma glucose (FPG) of Korean T2DM patients.

2.3 BENEFIT-RISK ASSESSMENT

Patients will be managed according to the local practice guidelines. The choice of treatment will be solely at the discretion of the participating physician. Trajenta will be administered according to the approved label in Korea. Hence there are no additional risks to patients by participating in this rNIS.

3. DESCRIPTION OF DESIGN AND STUDY POPULATION

3.1 OVERALL DESIGN AND PLAN

This rNIS is a prospective, non-interventional, open-label, multi-centre study. As per regulation, the re-examination period extends from 14 Sep 2011 until 13 Sep 2017 (6 years). However, active enrollment is to be initiated in 2012 after finalizing the re-imbursement agreement with the authority. Before initiation of the study, any newly reported adverse events collected from other sources such as spontaneous cases, literature cases etc will be closely monitored. The last patient follow up is expected in 2016.

3.1.1 Administrative structure of the study

This study will be managed by a project manager of Boehringer Ingelheim Korea. Data management and statistics will be outsourced to a qualified contract research organization (CRO).

3.2 DISCUSSION OF STUDY DESIGN

This is a single arm study with linagliptin.

Loss to follow up

All efforts will be made to minimize loss to follow up, particularly in the tracking of lost patients. To the extent possible, occurrence of adverse event, at minimum, for patients lost to follow up will be obtained. This allows assessing the impact of informative censoring due to treatment discontinuation. Also, patients lost to follow up will be characterized compared to the remaining patients and reason and time point of loss to follow up will be evaluated.

Channeling bias

Channeling bias can occur due to preferential prescribing in relation to different risks for the events of interest: e.g., if linagliptin would be more often prescribed to higher risk patients compared to other treatments, higher incidences of outcome events were then expected in the linagliptin group.

Confounding

As in any observational study, confounding may affect the estimation of associated between drug exposure and outcome of interest and statistical techniques. However, as only major confounders for selected research questions can be captured, residual (unmeasured) confounding may remain.

3.3 SELECTION OF POPULATION

A total of 3,000 patients will be enrolled at approximately 80 sites by as many as 100 or more NIS physicians. To minimize the selection bias at the site level, the goal is to have participating centers reflect a balance between general hospitals and clinics for surveillance. The treating physicians will mainly be internists. To minimize the selection bias, consecutive patients from each site who meet inclusion criteria will be enrolled in this study.

3.3.1 Main diagnosis for study entry

Patients diagnosed with T2DM will be included.

3.3.2 Inclusion criteria

- Patients who have been started on Trajenta in accordance with the approved label in Korea
- Patients who have signed on the data release consent form

3.3.3 Exclusion criteria

- Patients with previous exposure to Trajenta
- Current participation in clinical trials

3.3.4 Removal of patients from therapy or assessments

3.3.4.1 Removal of individual patients (therapy or assessments)

This section is not applicable.

3.3.4.2 Discontinuation of the study by the sponsor

Boehringer Ingelheim Korea reserves the right to discontinue the study overall or at a particular study site at any time for the following reasons:

1. Emergence of any effectiveness/safety information that could significantly affect continuation of the study
2. Violation of applicable local regulations, the NIS protocol, or the contract by a study site or participating physician, disturbing the appropriate conduct of the study.

4. TREATMENTS

4.1 PRESCRIBED TREATMENTS TO BE OBSERVED

4.1.1 Identity of test product(s) and comparator product(s)

Trajenta will be prescribed according to the local label and at the discretion of the treating physician. Since this is a non-interventional study, the drug will not be supplied by the sponsor. Furthermore, the sponsor will not cover the expenses related to other medications taken by the patient, interventions, procedures, or diagnostic tests.

4.1.2 Method of assigning patients to treatment groups

The choice of treatment is fully at the discretion of the physician and the patient. There is no treatment assignment by a third party.

4.1.3 Selection of doses in the study

Linagliptin will be administered 5 mg once a day which is within the authorized label in Korea.

4.1.4 Drug assignment and administration of doses for each patient

The physicians indicate doses and timing.

4.2 CONCOMITANT THERAPY, RESTRICTIONS, AND RESCUE TREATMENT

The protocol will allow additional drugs considered necessary for the patient's welfare to be prescribed at the discretion of the treating physician. It is required, however, to record the details of all concomitant medication administered to the patient during the course of treatment in eCRF. This includes concomitant therapies started one month prior to Trajenta initiation until the patient completes the final follow-up visit.

4.2.1 Rescue medication, emergency procedures, and additional treatment(s)

Please refer to the current local label.

4.2.2 Restrictions

4.2.2.1 Restrictions regarding concomitant treatment

Please refer to the current local label.

4.2.2.2 Restrictions on diet and life style

Please refer to the current local label.

5. VARIABLES AND THEIR ASSESSMENT

5.1 SAFETY

5.1.1 Endpoint(s) of safety

All reported adverse events including hypoglycemic events in patients who take at least one dose of Trajenta will be noted.

Hypoglycemic events include the overall hypoglycemic events, symptomatic hypoglycemia, confirmed hypoglycemia, nocturnal hypoglycemia, and severe hypoglycemia.

Endpoints pertaining to safety will be presented as incidence rates of adverse events and will include:

- adverse events
- unexpected adverse events
- serious adverse events
- drug-related adverse events
- adverse events leading to discontinuation
- adverse events by intensity, outcome of the event, causality

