8.4.2 Documentation of adverse events and patient narratives

Expedited reporting of serious adverse events, e.g. suspected unexpected serious adverse reactions (SUSARs) to health authorities and IECs/IRBs, will be done according to the local regulatory requirements.

For each AE, the investigator will provide the onset, end, intensity, outcome, seriousness and action taken with Trajenta tablets. The investigator will determine the relationship of Trajenta tablets to all AEs as defined in the 'Adverse Event Reporting' section of the physician binder.

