4.2 Safety Endpoint

- The incidence proportion of all AEs

5. Assessment Criteria

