5.2 Safety Assessment Criteria

- All AEs which is occurred at least once after administration of Trajenta.

6. Statistical Analyses

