6.3.2 Adverse Events by Preferred Terms

All AEs recorded in the CRF will be classified by body organs and terms under the classification standard of MedDRA terms, and all AEs excluding the AEs where causal relationship with Trajenta is “Unlikely” will be treated as AEs which causality cannot be excluded (hereafter “Adverse Drug Reaction(ADR)”).

For subjects to whom AE occurred, the incidence proportion of AEs and the number of AEs will be summarized.

Details are as follows.

- ① The frequency and percentage of the number of AEs according to serious adverse event, intensity, outcome of the event, action taken, causality, therapy of the event will be calculated.
- ② All AEs will be classified into the preferred terms according to serious adverse event, intensity, outcome of the event, action taken, causality, therapy of the event. The frequency and percentage of the number of each AE will also be calculated.
- ③ The number of subjects and the number of AE/ADR, Serious AE/Serious ADR, unexpected AE/ADR, unexpected Serious AE/unexpected Serious ADR will be calculated according to the preferred terms. In this case, the following subgroups are presented separately. Also, the incidence proportion and its 95% confidence interval will be estimated.
 - All of safety analysis set
 - Short-term effectiveness analysis set (Administration of Trajenta less than 24 weeks)
 - Long-term effectiveness analysis set (Administration of Trajenta for 24 weeks or more)
 - Subjects in effectiveness analysis set who administered DPP-4 inhibitor before administration of Trajenta
 - Subjects in effectiveness analysis set who did not administer DPP-4 inhibitor before administration of Trajenta
- ④ Preferred terms of Serious AE/Serious ADR, unexpected AE/ADR will be presented respectively according to the proportion of AE in the local product document.
- ⑤ For subjects excluded from the safety analysis set[†], the number of subjects and the number of AE/ADR, Serious AE/Serious ADR, unexpected AE/ADR, unexpected Serious AE/unexpected Serious ADR will be calculated according to the preferred terms. Also, the incidence proportion and its 95% confidence interval will be estimated.

[†]Subject excluded from safety analysis set: ‘Subjects who have not taken Trajenta’ and ‘Follow-up failure’ of patients excluded from safety analysis sets will be excluded (Reflecting the Ministry of Food and Drug Safety (MFDS) guideline).

	CONFIDENTIAL :	Last Update Date

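### Protocol 5.1.1 names five hypoglycaemia categories without defining them, and the SAP has no hypoglycaemia endpoint, grouping rule or table

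*Protocol*

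**What the plan says.** The protocol's primary objective is safety (Protocol 2.2.1). Section 5.1.1, headed as the endpoints of safety, says that all adverse events, hypoglycaemic events among them, will be noted. It then adds: "Hypoglycemic events include the overall hypoglycemic events, symptomatic hypoglycemia, confirmed hypoglycemia, nocturnal hypoglycemia, and severe hypoglycemia". The next sentence is "Endpoints pertaining to safety will be presented as incidence rates of adverse events and will include", followed by six bullets on classes of adverse event. None of the bullets is a hypoglycaemia category. The synopsis mentions hypoglycaemic events under its safety criteria but gives no sub-categories.

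The SAP gives one safety endpoint (4.2), "The incidence proportion of all AEs", and one assessment criterion (5.2), "All AEs which is occurred at least once after administration of Trajenta". Its safety analyses (6.3) and list of safety tables (7.4) break adverse events down by baseline characteristics, preferred term, seriousness, expectedness, intensity, outcome, action taken, causality and treatment given. Hypoglycaemia is not mentioned.

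On data, Protocol 8.4.2 says that for each adverse event "the investigator will provide the onset, end, intensity, outcome, seriousness and action taken with Trajenta tablets"; relationship to the drug is assessed as well. Protocol 5.1.5, on other safety parameters, is marked as not applicable. The adverse event form is part of the eCRF (Attachment 1), which was not supplied.

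**The concern.** Hypoglycaemia is the one type of adverse event that the protocol singles out in its safety endpoint section, and it does so in five named forms. A reader of the final report would expect a result for each. If the SAP is followed exactly, the report will hold no pooled count of patients with hypoglycaemia. It will have no statement at all on symptomatic, confirmed or nocturnal events.

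This falls under the primary objective, for a drug that the protocol's introduction describes as carrying a low hypoglycaemia risk. If someone asks for these figures later, the events will have to be sorted by rules that neither document contains, chosen with the data in hand.

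**Working it through.** The plan states no figure on this point that could be reproduced, and no power or precision formula applies. The check traces each of the five categories from the protocol to the SAP with three questions. Is it defined in either document? Do the adverse event items listed in Protocol 8.4.2 identify it? Does the SAP plan a result for it?

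| Category | Defined | Identified by the listed items | Planned SAP result |
|---|---|---|---|
| Overall | No | Through the coded term only; no list of terms to pool | No pooled row; one row per preferred term (6.3.2, item 3) |
| Symptomatic | No | No symptom item listed | None |
| Confirmed | No | No glucose value listed, no threshold given | None |
| Nocturnal | No | Onset is listed, but clock time is not stated and no night window is given | None |
| Severe | No | General intensity grade only | Event counts by preferred term and intensity (6.3.2, item 2) |

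Count: defined 0 of 5; dedicated SAP analysis 0 of 5; rough stand-in 2 of 5 (overall, severe); no planned result 5 − 2 = 3 of 5.

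**Overall.** Item 3 of SAP 6.3.2 gives subjects and events for each preferred term, and says "Also, the incidence proportion and its 95% confidence interval will be estimated". If every hypoglycaemic event were coded to a single term, that row would be the overall incidence. With two terms A and B, patients with at least one event = n(A) + n(B) − n(A and B). The table gives n(A) and n(B) but not the overlap. Adding the rows therefore counts a patient with both terms twice, and the interval for the pooled proportion cannot be built from the separate rows.

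**Severe.** Item 2 says "All AEs will be classified into the preferred terms according to serious adverse event, intensity, outcome of the event, action taken, causality" and then "The frequency and percentage of the number of each AE will also be calculated". The unit is the event, so the table gives no proportion of patients with a severe event. The intensity scale in Protocol 5.1.2.1 is the general one for all adverse events. Its top grade refers to interference with daily activities and to stopping the drug. Neither document says whether severe hypoglycaemia is meant in that sense.

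**Symptomatic, confirmed, nocturnal.** No breakdown in SAP 6.3 or 7.4 corresponds to any of these. For confirmed events, Protocol 7.4 adds that no investigations are required, so a glucose value at the time of an event is not assured.

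**Background therapy.** SAP 3.1 expects combinations with sulfonylurea and insulin. SAP 6.3.1 compares adverse events by other anti-diabetic agent, but only for adverse events as a whole. The preferred-term subgroups in 6.3.2 are duration of administration and prior DPP-4 inhibitor use. No planned table shows hypoglycaemia by these co-medications.

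**The case against.** The strongest reply is that the protocol does not clearly make the five categories reportable endpoints. The sentence can be read as describing what is collected. The sentence that governs presentation is followed by six bullets without hypoglycaemia, and the SAP covers nearly all of those. This has weight, and the passage is ambiguous. Yet the sentence stands in the endpoint section, directly before the statement on presentation, and a five-way list serves little purpose if only totals over all adverse events are reported.

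A second reply is that hypoglycaemia will be reported anyway. This is partly right. A reader might infer that the SAP analyses none of the categories, or that four of the five will have no estimate of any kind. The documents do not support that: every hypoglycaemia preferred term gets an incidence proportion and interval, and intensity is tabulated by event.

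A third reply concerns the data. A reader might infer from Protocol 8.4.2 that the recorded fields cannot separate the categories. That is not shown. The SAP tabulates treatment given for the event, which is absent from the 8.4.2 list, so that list is incomplete. The eCRF and site materials may hold glucose, symptom or clock-time fields. What stands is that the listed items do not by themselves identify the categories.

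Finally, the study is descriptive, with no confirmatory hypothesis (Protocol 7.1). That lowers the stakes, but a descriptive endpoint still needs a definition and a table.

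**Conclusion.** The point holds as a gap between protocol and SAP. Five categories are named and none is defined. None has a dedicated analysis, two have rough stand-ins and three have no planned result. It should be closed before the final report. It does not threaten the study as a whole, because individual hypoglycaemia terms will still be reported with intervals.

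The conclusion rests on reading the five-category sentence as part of the endpoint section in which it stands, and on the SAP text supplied. It makes no claim about what the eCRF records. If the eCRF holds the needed fields, the omission is easier to repair but remains an omission. If it does not, some categories cannot be derived and the report should say so.

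A reader might also infer that the protocol requires hypoglycaemia by background sulfonylurea or insulin. It does not. That split would be a useful addition from data already collected.

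**What to change.** Add a hypoglycaemia table to SAP 4.2, 6.3 and 7.4. For overall hypoglycaemia, give the number of patients with at least one event, the number of events, the incidence proportion and its 95% CI. Count each patient once across a stated list of preferred terms. Give the same row for each other named category that the eCRF fields support, with its definition, the fields used and the assignment rule fixed before the final analysis.

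Report a category that the data cannot support as not derivable, with the reason. Removing it from the endpoint list at this stage would be less transparent. Optionally, show the overall row by background sulfonylurea or insulin use.

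The cost is one table and a classification step on existing records, with no new patients or procedures. There are two drawbacks. Some categories may prove underivable. The rules would also come late: last follow-up was expected in 2016 (SAP 2.1) and SAP version 3.0 is dated 21 August 2017, so rules written after follow-up should be labelled as such in the report.

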6.3 Safety Analyses

In the safety analysis set, the number of subjects with AEs and the number of AEs will be calculated. Also, the incidence proportion of AEs will be estimated with its 95% confidence interval.

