7.4 Safety Analyses

- According to the baseline characteristics, incidence proportion and the number of AEs (frequency and percentage)
- The number of AEs for serious adverse event, intensity, outcome of the event, action taken, causality, therapy of the event (frequency and percentage)
- The number of AEs for serious adverse event, intensity, outcome of the event, action taken, causality, therapy of the event by preferred terms (frequency and percentage)
- For safety analysis set, according to whether or not administered Tragenta for more than 24 weeks and whether or not administered DPP-4 inhibitor before administration of Trajenta, the number of AE/ADR, Serious AE/Serious ADR, unexpected AE/ADR, unexpected Serious AE/unexpected Serious ADR by preferred terms (frequency, percentage, incidence proportion and its 95% confidence interval)
- Preferred terms of Serious AE/Serious ADR, unexpected AE/ADR according to the proportion of AE

	CONFIDENTIAL :	Last Update Date
	THIS DOCUMENT AND INFORMATION CONTAINED HEREIN IS PROPRIETARY TO COMPANY AND IS NOT TO BE DISCLOSED WITHOUT THE WRITTEN PERMISSION OF COMPANY.	21-AUG-2017
STATISTICAL ANALYSIS PLAN(V3.0)		

- For subjects excluded from the safety analysis set[†], the number of AE/ADR, Serious AE/Serious ADR, unexpected AE/ADR, unexpected Serious AE/unexpected Serious ADR according to the preferred terms (frequency, percentage, incidence proportion and its 95% confidence interval)
- Multiple logistic regression analysis on the incidence proportion of AEs
 - †Subject excluded from safety analysis set: ‘Subjects who didn’t receive Trajenta’ and ‘Follow-up failure’ of patients excluded from safety analysis sets will be excluded (Reflecting the Ministry of Food and Drug Safety (MFDS) guideline).

8. Note

- Each statistical analysis will be carried out with SAS Software version 9.4 or more recent version.
- In the descriptive statistics, mean, SD, median, minimum and maximum will be calculated for continuous variables, and frequency and percentage for categorical variables.
- Data including sign of inequality such as “≥20”, “>20” will be excluded from analysis.
- All test statistics will be the results of two-sided tests with the statistical significant level of 0.05.
- The followings shall be included only in re-examination report:
 - Estimation of 95% confidence interval for incidence proportion of AEs by baseline characteristics

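### The SAP plans no patient-level incidence for AEs leading to discontinuation or for AEs by intensity (or outcome), although the protocol lists these as incidence endpoints

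*Protocol*

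**What the plan says.** Monitoring safety is the primary objective in both documents. Protocol 5.1.1 sets the scale for its safety endpoints: "Endpoints pertaining to safety will be presented as incidence rates of adverse events and will include". The list that follows contains "adverse events leading to discontinuation" and "adverse events by intensity, outcome of the event, causality".

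SAP 4.2 reduces this list to one endpoint, "The incidence proportion of all AEs". SAP 6.3 gives the overall analysis, in which "the incidence proportion of AEs will be estimated with its 95% confidence interval".

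The finer breakdowns are in SAP 6.3.2. Item ① plans "The frequency and percentage of the number of AEs according to serious adverse event, intensity, outcome of the event, action taken", continuing with causality and treatment of the event. Item ② repeats this by preferred term, again counting events. Item ③ differs: for AEs, ADRs, and serious and unexpected AEs and ADRs, it asks for number of subjects, number of events, incidence proportion and 95% CI.

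The table list in 7.4 keeps the same division. The item ③ table carries incidence and intervals. The table for the other attributes does not: "The number of AEs for serious adverse event, intensity, outcome of the event, action taken, causality, therapy of the event (frequency and percentage".

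**The concern.** The two documents use different scales for the same endpoints. An incidence counts patients with at least one event against the patients at risk. Items ① and ② count events, and their wording points to all AEs as the base. On that base, a patient who reports many mild events lowers the percentage of severe events and of events with the drug stopped, although nobody's risk has changed.

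The proportion of patients who stop Trajenta because of an AE, and the proportion with a severe AE, are basic tolerability results. If the SAP is followed as written, the report on the primary objective contains neither as a planned estimate with an interval. The only percentages beside those labels would be shares of events.

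**Working it through.** **1. Each listed endpoint against the SAP**

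| Protocol 5.1.1 endpoint | Planned in the SAP | Subjects, incidence and 95% CI? |
|---|---|---|
| All AEs | 4.2, 6.3 | Yes |
| Unexpected AEs | 6.3.2 item ③ | Yes |
| Serious AEs | 6.3.2 item ③ | Yes |
| Drug-related AEs | 6.3.2 item ③, as ADRs | Yes |
| AEs leading to discontinuation | Not named; nearest is action taken in items ① and ② | No |
| AEs by intensity | Items ① and ② | No |
| AEs by outcome | Items ① and ② | No |
| AEs by causality | Related or not: item ③, as ADRs. Single categories: items ① and ② | Related or not: yes. Single categories: no |

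The ADR row holds because 6.3.2 treats every AE as an ADR unless its causality was judged unlikely. That is the same split into related and unrelated as in protocol 5.1.2.1.

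**2. What a share of events says about patients**

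The documents state no AE rate, so there is no planned figure to reproduce. All counts below are assumptions except N = 3,000, which is the enrolment target (protocol 7.6). The safety set will be smaller after the exclusions in SAP 3.1. Intervals are exact (Clopper-Pearson).

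Share of events = AEs with the attribute / all AEs. Incidence proportion = patients with at least one such AE / patients in the safety set.

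Assume 300 patients have 450 AEs in total, and 60 patients stop the drug for one AE each.

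- Share of events: 60/450 = 13.3%.
- Incidence proportion: 60/3,000 = 2.0% (95% CI 1.53 to 2.57).
- If the same 300 patients report 150 further mild AEs, the share falls to 60/600 = 10.0%. The incidence proportion stays at 2.0%.

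**3. The same share, different risks**

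Fix the share at 10% of AEs with the drug stopped, and vary the rest.

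| Patients with an AE | AEs per affected patient | All AEs | AEs with drug stopped | Such AEs per stopping patient | Patients stopping | Incidence (95% CI) |
|---|---|---|---|---|---|---|
| 5% (150) | 1.5 | 225 | 22.5 | 2 | 11 | 0.37% (0.18 to 0.66) |
| 5% (150) | 1 | 150 | 15 | 1 | 15 | 0.50% (0.28 to 0.82) |
| 10% (300) | 2 | 600 | 60 | 1 | 60 | 2.00% (1.53 to 2.57) |
| 30% (900) | 2 | 1,800 | 180 | 1 | 180 | 6.00% (5.18 to 6.91) |

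In the first row, 22.5/2 = 11.25 is rounded to 11. The ratio of the last incidence to the first is 180/11, about 16.

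A reader can partly narrow this range, because the overall AE incidence and number of AEs will be reported. The number of such events per stopping patient remains unknown. At 10% of patients with an AE and 2 AEs each, the 60 events could belong to 60 patients (2.00%, 1.53 to 2.57) or, at two events each, to 30 (1.00%, 0.68 to 1.42).

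**The case against.** **The opening of 6.3.2 already promises incidence.** It says: "For subjects to whom AE occurred, the incidence proportion of AEs and the number of AEs will be summarized". The items that follow are introduced as its details, and they carry incidence to the item ③ categories only. Since item ③ asks for subjects and intervals explicitly, their absence from items ① and ② reads as deliberate. It is true that the SAP does not state the denominator for items ① and ②. Even with patients as the base, the numerator would be events, so the result would not be an incidence proportion.

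**Discontinuation is covered by the reasons for withdrawal.** SAP 6.1 and 7.2 summarise the reason for premature study withdrawal by patient, and this stands in part. If AE is one of the reasons, a patient count will appear. But the categories are not listed, leaving the study is not the same as stopping the drug, the table is not linked to AE records, and no interval is planned. Section 6.3.1 may also give AE incidence within each withdrawal reason, but that is not the incidence of stopping because of an AE.

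**The protocol does not define its incidence rates.** This is correct: it gives no denominator and no rule of one count per patient. A breakdown by outcome can fairly be read as a description of events, because outcome belongs to an event and one patient's events may end differently. That makes patient-level tables by outcome optional. It does not help for discontinuation or intensity, since a share of events is neither a risk per patient nor a rate per person-time.

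**The study is descriptive and the main figures are there.** This also stands. Overall, serious, unexpected and drug-related AEs have patient-level incidence, no hypothesis is tested, and the disputed tables are labelled as numbers of AEs. It limits the weight of the point but does not remove it.

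**Conclusion.** The point holds for AEs leading to discontinuation and for intensity. The protocol lists both as incidence endpoints under the primary objective, and the SAP plans no subject count, incidence proportion or CI for either. It holds formally for outcome too, where the practical loss is small.

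Two stronger readings are tempting, and the documents support neither. A reader might infer that causality also lacks any patient-level estimate. It does not: item ③ gives drug-related incidence with an interval, and only the single causality categories are missing. A reader might also infer that no patient count for discontinuation could ever emerge. The table of withdrawal reasons may supply a partial one.

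The size of the gap cannot be fixed from the documents, which give no AE rates. The contrast of 13.3% with 2.0%, and the range of 0.37% to 6.0% for one share of events, rest on assumed counts and on N = 3,000 before exclusions. The conclusion that a share of events does not determine the proportion of patients affected does not depend on those counts. This is a gap in table specification that should be closed. It does not threaten the main AE results.

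**What to change.** In SAP 6.3.2 and in the 7.4 table list, add number of subjects, incidence proportion and 95% CI, with the safety set as denominator, for:

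- AEs leading to discontinuation of Trajenta, counting a patient once if at least one AE has the drug recorded as stopped under action taken;
- worst intensity per patient (mild, moderate, severe).

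Name both in SAP 4.2 so that it matches protocol 5.1.1, and state the CI method for AE incidence. The SAP names the exact method only for the effectiveness rate. Keep the event counts in items ① and ② alongside, and state their denominator. Patient-level tables by outcome and by single causality category are optional; if outcome is included, a rule is needed for patients whose events end differently.

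The cost is one or two added tables. Protocol 8.4.2 already has intensity, outcome and action taken with Trajenta recorded for each AE, so no new data are needed. This assumes that the categories of action taken, which the documents do not list, include stopping the drug.
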